5.3. Study Rationale

The purpose of this study is to evaluate the safety, tolerability and PK of delivering 2 doses of anifrolumab via the subcutaneous (SC) route of administration (ROA) and 1 dose of anifrolumab via IV route in healthy subjects. One of the doses to be studied is a large volume SC injection, to obtain early information on the feasibility of developing a large volume SC device for the anifrolumab program that could support less frequent administration. Developing a SC ROA for anifrolumab will provide patients more flexibility in their dosing options and may improve accessibility and compliance. Inclusion of an IV arm will allow for a comparison of the PK in healthy subjects with subjects with SLE, in whom SC doses of anifrolumab have never been tested before.

5.4. Dose Rationale

The following doses have been selected for this study: 300 mg IV, 300 and 600 mg SC doses. In the phase 2 study of anifrolumab in patients with moderate to severe SLE, the 300 mg and 1000 mg doses met the primary endpoint of achieving a SLE responder index (SRI) 4 (SRI4) response and reduction of corticosteroid dose to ≤ 7.5 mg/day at day 169. These results were consistent across multiple measures of efficacy including British Isles Lupus Assessment Group (BILAG)-based Combined Lupus Assessment (BICLA) response, Cutaneous Lupus Erythematosus Disease Area and Severity Index (CLASI) in patients who had a CLASI score >10 at baseline, and reduction in flare rate. Although numbers were small, there were more patients who developed herpes zoster in the 1000 mg group than in the

300 mg group, therefore the 300 mg dose was selected as the preferred dose for further study. Although there is currently no PK data available in normal subjects, the PK of anifrolumab was similar in 2 different patient populations (SSc and SLE) and in several racial groups (Japanese subjects). The sponsor expects that the PK in normal subjects will be similar to PK data obtained previously.

Developing a SC dose is expected to offer flexibility in meeting patients' dosing needs. PKPD model-based simulations have indicated that doses of 150-300 mg SC administered every 2 weeks and 300-600 mg SC administered every 4 weeks will result in equivalent reduction in gene signature PD marker compared to the target dose of 300 mg IV. Based on these simulations, doses of 300 and 600 mg SC have been selected for PK evaluation in this study. A dose of 300 mg represents the highest feasible syringe injection dose and a dose of 600 mg represents a large volume injection.

5.5. Previous Clinical Experience

A phase 3 program with anifrolumab IV in patients with moderate to severe SLE was initiated 3Q2015. A phase 2 program with anifrolumab IV in patients with active proliferative Lupus Nephritis was initiated 4Q2015. The clinical experience from 4 prior MedImmune/AstraZeneca-sponsored clinical studies (Study MI-CP180, CD-IA-MEDI-546-1013, CD-IA-MEDI-546-1145, and) in adult subjects with SSc or SLE are summarized below:

- The first clinical study of anifrolumab was a Phase 1, multicenter, open-label, dose-escalation study to evaluate the safety and tolerability of single and multiple IV doses of anifrolumab in adult patients with SSc who had skin thickening in an area suitable for repeat biopsy (Study MI-CP180). A total of 34 patients were evaluated in the study: 21 patients received 1 of 6 single IV doses of anifrolumab (0.1, 0.3, 1.0, 3.0, 10.0, or 20.0 mg/kg), and 13 patients received 1 of 3 multiple IV doses of anifrolumab (0.3, 1.0, or 5.0 mg/kg/dose every week × 4 doses). The most common TEAEs in Study MI-CP180 (seen in more than 10% of patients) were upper respiratory tract infection (URTI), headache, diarrhea, nausea, arthralgia, fatigue and pruritus.
- A Phase 2, randomized, double-blind, placebo-controlled, parallel group study to evaluate the efficacy and safety of anifrolumab in adult patients with chronic, moderately-to-severely active SLE with an inadequate response to standard of care treatment for SLE (Study CD-IA-MEDI-546-1013) has been completed. Three hundred and seven patients were randomized in a 1:1:1 ratio to receive a fixed IV dose of anifrolumab (300 or 1000 mg) or placebo every 4 weeks (q4wks) for 48 weeks for a total of 13 doses. The most common TEAEs in study

CD-IA-MEDI-546-1013 (seen in more than 10% of patients) were headache, URTI, nasopharyngitis and urinary tract infection.

- A Phase 2, open-label extension (OLE) study to evaluate long-term safety of anifrolumab in adults with SLE is ongoing (Study CD-IA-MEDI-546-1145). All patients who completed Study CD-IA-MEDI-546-1013 and met the OLE study criteria were enrolled. The most common AEs in Study CD-IA-MEDI-546-1145 (seen in more than 5% of patients) have been nasopharyngitis and bronchitis.
- A Phase 2, multicenter, open-label, dose-escalation study to evaluate the safety and tolerability of anifrolumab in adult Japanese patients with active SLE () is ongoing. Approximately 15 patients were planned to receive a fixed IV dose of anifrolumab (100-, 300-, or 1000-mg) q4wks for 48 weeks, for a total of 13 doses, followed by a fixed IV dose of anifrolumab (300 or 1000 mg) q4wks for 104 weeks for a total of 27 doses. The most common TEAEs in Study (seen in more than 20% of patients) (stages 1 and 2) have been nasopharyngitis, upper abdominal pain URTI, headache and SLE.

Important potential risks include serious viral and bacterial infections, including viral reactivation (particularly herpes zoster) and opportunistic infections, malignancies, infusion-related reactions, severe hypersensitivity reactions, including anaphylaxis and immune complex disease/vasculitis. Potential risks include drug-drug interactions and vaccine-drug interactions.

As with the administration of any immunoglobulin, hypersensitivity reactions and acute immunoglobulin E (IgE)-mediated allergic (anaphylaxis) reactions may occur, which may be severe and may result in death. Acute allergic reactions may include hypotension, dyspnea, cyanosis, respiratory failure, urticaria, pruritus, angioedema, hypotonia, and unresponsiveness. Acute severe allergic reactions (anaphylaxis) usually occur soon after exposure, usually within 10 minutes. Subjects may experience paresthesia, hypotension, facial, laryngeal or pharyngeal angioedema, mental status changes, flushing, urticaria, pruritus, gastrointestinal symptoms, airway obstruction, bronchospasm, and wheezing.

Although anifrolumab is a human mAb, there is still a chance that humans could develop anti-drug antibodies (ADAs). The occurrence of such ADAs can result in immune complex disease (with manifestations such as arthralgia, serum sickness, and vasculitis) or altered anifrolumab levels or pharmacologic activity/efficacy. Subjects will be monitored clinically for symptoms associated with immune reactivity and for the presence of such antibodies.

Anifrolumab has been administered IV in clinical studies conducted to date. Potential risks associated with IV administration of anifrolumab are infection, redness, swelling, pain, and induration at the administration site. These types of reactions have not been reported to date.

5.6. Risk-benefit Assessment

There are no direct benefits for the subjects participating in this study.

In study CD-IA-MEDI-546-1013, anifrolumab demonstrated a clinically relevant benefit in patients with moderate to severe SLE treated with standard-of-care. The efficacy was supported by a broad range of clinical measures of global (various levels of SRI responses, BICLA) and organ-specific disease activity (CLASI, joint count). A clinically relevant increase in the proportion of patients achieving pre-specified corticosteroid reduction in the 300-mg group was also observed compared with placebo.

Anifrolumab was generally well tolerated. The proportion of patients receiving anifrolumab and experiencing herpes zoster reactivation was greater compared to placebo. A dose-related increase in the proportion of patients with uncomplicated cutaneous herpes zoster infections was also observed in patients receiving anifrolumab (either 300 mg or 1000 mg). Uncomplicated herpes zoster is considered an identified risk.

To minimize this risk for the current healthy subject study, subjects with any severe herpes infection at any time prior to dosing, including, but not limited to, disseminated herpes (ever; greater than 3 dermatomes), herpes encephalitis (ever), recurrent herpes zoster (defined as 2 episodes within 2 years) or ophthalmic herpes (ever) or any herpes zoster infection that has not completely resolved within 12 weeks prior to screening will be excluded from the study.

To date, in clinical trials of IV administration of anifrolumab, hypersensitivity events or anaphylaxis/anaphylactoid events have not occurred more frequently in patients who were treated with anifrolumab as compared to placebo, although careful monitoring for such events will continue.

Although arteritis was detected in the monkey toxicology studies, to date no signal for an increased risk of vasculitis or arteritis has been detected in human clinical studies, although this continues to be followed as an adverse event (AE) of special interest (AESI).

The administration of any foreign protein may be associated with acute allergic reactions that may be severe and may result in death. Acute allergic reactions may include hypotension, dyspnea, cyanosis, respiratory failure, urticaria, pruritus, angioedema, hypotonia and unresponsiveness. Reports of infusion-related reactions from clinical trials conducted to date

suggest that the frequency, severity and characteristics of these reactions are similar across all treatment groups.

The current study with SC administration in healthy subjects will be conducted in an experienced clinical pharmacology unit with trained staff and adequate equipment to handle any hypersensitivity events. Although there is no potential benefit for healthy subjects to receive anifrolumab, the overall safety and tolerability profile of anifrolumab support administration of a single dose to normal subjects for the purposes of assessing safety, tolerability and PK.

Although anifrolumab is a human monoclonal antibody, there is still a chance that humans could develop anti-anifrolumab antibodies. The occurrence of such ADAs can result in acute or delayed hypersensitivity reactions, including anaphylaxis or immune complex disease (with manifestations such as arthralgia, serum sickness and vasculitis) or altered anifrolumab levels or pharmacologic activity/efficacy.

In order to minimize the risk of treatment with anifrolumab, subjects with risk factors for serious infection, malignancy, or immune deficiency disorders are specifically excluded from participation in this study.

Additionally, serious infections, including non-opportunistic serious infections, opportunistic infections, anaphylaxis, malignancy, herpes zoster, tuberculosis (TB) (including latent TB), influenza vasculitis (non-SLE) and major adverse cardiovascular events (MACE) (including myocardial infarction [MI], stroke, acute coronary syndrome, or cardiovascular death) are designated as AESIs in this study.

In conclusion, AstraZeneca believes that the available nonclinical and clinical data indicate an acceptable safety profile for anifrolumab. The proposed dosing regimens for Protocol are adequately justified and the management plan for potential risks associated with anifrolumab is appropriate. The emerging safety profile has not identified any risks that would preclude continued investigation of anifrolumab. AstraZeneca believes that anifrolumab continues to demonstrate an overall positive benefit-risk balance to support its further clinical evaluation.

AstraZeneca will immediately notify the investigator of important safety data that becomes available during the study.

6. STUDY OBJECTIVES

6.1. Primary Objectives

- To evaluate the PK of a single administration of 2 doses of subcutaneously and 1 dose of intravenously dosed anifrolumab in healthy subjects.
- To evaluate the safety and tolerability of subcutaneously and intravenously dosed anifrolumab in healthy subjects.

6.2. Secondary Objective

- To evaluate the immunogenicity of subcutaneously and intravenously dosed anifrolumab in healthy subjects.

Refer to [Section 11.9.1](#) for PK parameters and [Section 9.3](#) for safety variables.

7. OVERALL DESIGN AND PLAN OF THE STUDY

7.1. Overall Study Design

This study will be a Phase 1, single-center, double-blind, randomized, placebo-controlled study to evaluate the safety, tolerability and PK of 2 dose levels of SC administered and 1 dose level of IV administered anifrolumab in healthy subjects.

The study will comprise:

- A screening period of maximum 28 days;
- One treatment period during which subjects will be resident prior to the evening meal the night before dosing with anifrolumab or placebo (Day -1) until at least 48 hours after dosing; discharged on the morning of Day 3;
- Follow-up visits on Days 5, 8, 11, 15, 22, 29, 42 and 57 with a final visit on Day 85.

7.1.1. End of study

The end of study is defined as the last subject's last visit to the clinical unit.

7.1.2. Interim analyses

No interim analyses will be performed in this study.

[figure not shown]
7.1.3. Expected duration of the study

Each subject will be involved in the study for approximately 16 weeks.

7.2. Study Flow Chart and Schedule of Assessments

The flow of events is illustrated in [Figure 1](#) for all treatments, depending on the subject's assigned randomization (refer to [Section 8.9.2](#)).

Figure 1 Study Flow Chart

The Schedule of Assessments displaying assessments/tasks and time points is presented in [Table 1](#).

Table 1 Schedule of Assessments

Study Plan	Visit 1	Visits 2		Visits 3 to 10	Visit 11
	Screening	Day -1	Dosing Session Days 1 to 3	Follow-up visits ^a	Final Follow-up Visit (Day 85 ± 2 days)
Informed consent	X				
Inclusion/exclusion criteria	X	X			
Demographic data	X				
Weight, height, BMI	X	X (weight)			
Medical history	X				
Concomitant medication	X	X	X	X ^a	X
Urinary drug screen	X	X			
Viral Serology	X				
Pregnancy and FSH (females only)	X	X ^b			X ^b
Pap smear (females only)	X ^c				
IGRA (QuantiFERON-TB GOLD)	X				
Serum alcohol screen	X	X			
Randomization			X		
Study residency:					
Check-in		X			
Check-out			Day 3 (48h post-dose)		
Non-residential visit	X			X ^a	X
IMP administration:					
			Day 1 (0h)		
Pharmacokinetics:					
Blood samples for Anifrolumab			Pre-dose, at 5 minutes after end IV infusion ^d and at 24 and 48 hours post-dose	X ^a	X
Safety and tolerability:					
Local injection site pain (VAS) assessment ^e			Immediately after dosing, at 10, 20 and 30 minutes and at 1, 2, 4, 8, 24 and 48 hours after injection		
Local injection site pruritus (VAS) assessment ^e			Immediately after dosing, at 10, 20 and 30 minutes and at 1, 2, 4, 8, 24 and 48 hours after injection		

Study Plan	Visit 1	Visits 2		Visits 3 to 10	Visit 11
	Screening	Day -1	Dosing Session Days 1 to 3	Follow-up visits ^a	Final Follow-up Visit (Day 85 ± 2 days)
Local injection site reaction (erythema, induration) assessment ^e			Immediately after dosing, at 10, 20 and 30 minutes and at 1, 2, 4, 8, 24 and 48 hours after injection		
Adverse event questioning	Only SAEs	X	X	X ^a	X
Physical examination	X (full)	X (brief)			X (full)
Blood pressure, pulse rate and oral temperature	X	X	Pre-dose and at 48 hours post-dose	X	X
12-lead Safety ECG	X	X	Pre-dose and at 48 hours post-dose		X
Clinical laboratory assessments ^h	X	X		X ^f	X
Immunogenicity:					
ADA			Pre-dose	X ^g	X

^a Days 5, 8, 11, 15, 22, 29, 42 and 57. The follow-up visits should all be performed at approximately the same time of day based off of Day 1 dosing (± 1 day for Days 5, 8, 11 and 15 and ± 2 days for Days 22, 29, 42 and 57).

^b Pregnancy screen

^c Pap smear allowed anytime during the screening period as long as result is back prior to randomization.

^d For Cohort 2 only, a sample should be drawn 5 minutes after the completion of IV infusion (including the saline flush)

^e Only in subjects who receive dose subcutaneously (Cohorts 1 and 3). Will be followed until event is resolved, if applicable.

^f Day 29

^g Days 5 and 29

^h Includes hematology, serum clinical chemistry and urinalysis. See [Section 9.3.8](#).

7.3. Order of Assessments

It is important that PK sampling occurs as close as possible to scheduled time. In order to achieve this, other assessments scheduled at the same time may be initiated prior to the time point.

The sequence at a particular time point is:

1. ECGs
2. Vital signs (systolic and diastolic blood pressure [BP], pulse rate, oral temperature)

3. PK blood sampling (will be drawn at the specified time point)
4. Immunogenicity sampling
5. Clinical laboratory assessments
6. Local injection site pain, pruritus and reaction assessments (SC dosing only)

7.4. Restrictions During the Study

The following restrictions apply for the specified times during the study period:

1. Subjects should not engage in any strenuous activity from 72 hours prior to dosing on Day 1 and prior to each visit until after their final follow-up visit.
2. Subjects should abstain from alcohol for 72 hours prior to admission and each visit. During the follow-up period, subjects should consume no more than 2 units of alcohol per day and should abstain from alcohol for 72 hours before their final follow-up visit.
3. During in-house stay, subjects will receive a standard diet, which excludes all alcohol and grapefruit-containing products. No additional food or beverages must be consumed whilst in the clinical unit.
4. During the subjects' outpatient periods, subjects should abstain from consuming high energy drinks (e.g.,), and food containing poppy seeds (e.g., specialty breads and muffins) and any over-the-counter (OTC) medication or herbal preparations until after their final follow-up visit has been completed.
5. Subjects will be required to abstain from blood or plasma/serum donation until after the final follow-up visit (Day 85).
6. Medication restrictions

Refer to [Section 8.7](#).

7. Reproductive restrictions

- Female subjects

Women of childbearing potential must use 2 effective methods of avoiding pregnancy, one of which is a barrier method from screening until after the final follow-up visit (Day 85), unless the subject is surgically sterile (i.e., bilateral tubal ligation, bilateral oophorectomy, or complete hysterectomy), has a sterile male partner, is 1 year postmenopausal, or practices abstinence. Cessation of birth control after this period should be discussed with a responsible physician.

- Sustained abstinence is an acceptable practice; however, periodic abstinence, the rhythm method and the withdrawal method are not acceptable methods of contraception.
- Postmenopausal is defined as at least 12 months since last menses and the subject has an elevated follicle-stimulating hormone (FSH) level greater than the clinical laboratory value of post-menopausal at screening.

Methods of birth control:

- Barrier methods
 - Male condom plus spermicide*
 - Cap (with spermicide cream or jelly*)
 - Diaphragm (with spermicide cream or jelly*)

*Where commercially available
- Intrauterine Device methods
 -
 -
- Hormonal methods
 - Implants
 - Hormone shot or injection
 - Combined pill
 - Minipill
 - Patch
- Male subjects
 - Nonsterilized males who are sexually active with a female partner of childbearing potential must use a condom with spermicide (where commercially available) from Day 1 until after the final follow-up visit (Day 85).

- Sperm donation

Male subjects should not donate sperm for the duration of the study (Day 1 until after the final follow-up visit [Day 85]).

- Pregnancy

Subjects will be instructed that if their partner becomes pregnant during the study, this should be reported to the investigator. The investigator should also be notified of pregnancy occurring during the study but confirmed after completion of the study. In the event that a subject's partner is subsequently found to be pregnant after the subject is included in the study, then consent will be sought from the partner and if granted any pregnancy will be followed and the status of mother and/or child will be reported to the sponsor after delivery.

A pregnancy notification form and follow-up will be completed. Any SAE associated with the pregnancy, delivery or termination of the pregnancy will be reported as an SAE.

7.5. Selection of Study Population

The investigator should keep a subject screening log of all potential subjects who consented and were subjected to screening procedures.

Subjects who fail to meet the inclusion criteria or meet any exclusion criterion should not, under any circumstances, be randomized into the study. There can be no exceptions to this rule.

This study will be conducted in male and female subjects.

7.5.1. Inclusion criteria

For inclusion in the study, subjects should fulfill the following criteria:

1. Provision of signed and dated, written informed consent prior to any study specific procedures.
2. Healthy male and/or female subjects aged 18 – 55 years with suitable veins for cannulation or repeated venipuncture.
3. Females must have a negative pregnancy test at screening and on admission to the unit and must not be lactating.

If of non-childbearing potential, it must be confirmed at screening by fulfilling 1 of the following criteria:

Post-menopausal defined as amenorrhea for at least 12 months or more following cessation of all exogenous hormonal treatments and FSH levels in the post-menopausal range as per the clinical laboratory for this study.

Documentation is needed for irreversible surgical sterilization by hysterectomy, bilateral oophorectomy, bilateral salpingectomy, bilateral tubal occlusion or bilateral tubal ligation.

4. Females with an intact cervix must have documentation of a Pap smear with no documented malignancy (e.g., cervical intraepithelial neoplasia grade III [CIN III], carcinoma in situ [CIS], or adenocarcinoma in situ [AIS]) within 2 years prior to Day 1) (see [Appendix 15.4](#) for guidance on abnormal Pap smear results).
5. Have a body mass index (BMI) between 18 and 32 kg/m², inclusive, and weigh at least 50 kg.
6. Must have adequate abdominal adipose tissue for SC injection, as judged by the investigator.
7. No history of latent or active TB prior to screening.
8. No signs or symptoms suggestive of active TB from medical history or physical examination, including a negative IGRA test at screening.

Note: If the IGRA result is reported as indeterminate, then the test can be repeated once. If the repeat test result is reported as indeterminate, then the subject will not be included in the study.

9. No recent contact with a person with active TB.
10. A chest radiograph with no evidence of current active infection (e.g., TB) or old active TB, malignancy, or clinically significant abnormalities obtained during the screening period or anytime within 6 months prior to screening.

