26. Use of any prescribed or non-prescribed medication including antacids, analgesics (other than paracetamol/acetaminophen), herbal remedies, megadose vitamins (intake of 20 to 600 times the recommended daily dose) and minerals during the 2 weeks prior to the administration of IMP or longer if the medication has a long half-life.

Note: Hormonal replacement therapy is allowed for females.

27. Involvement of any AstraZeneca, PAREXEL or study site employee or their close relatives.
28. Judgment by the investigator that the subject should not participate in the study if they have any ongoing or recent (i.e., during the screening period) minor medical complaints that may interfere with the interpretation of study data or are considered unlikely to comply with study procedures, restrictions and requirements.
29. Vulnerable subjects, e.g., kept in detention, protected adults under guardianship, trusteeship, or committed to an institution by governmental or juridical order.
30. History of vasculitis.

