8.7. Concomitant Medication

Apart from paracetamol/acetaminophen, no concomitant medication or therapy will be allowed. The subjects should be instructed that no other medication is allowed, including herbal remedies, vitamin supplements and OTC products, without the consent of the investigator.

For females, hormonal replacement therapy is allowed.

Medication, which is considered necessary for the subject's safety and well-being, may be given at the discretion of the investigator during the residential period.

When any medication is required, it should be prescribed by the investigator. Following consultation with AstraZeneca Lead Physician, the investigator must determine whether or not the subject should continue in the study.

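### Section 7.4 and inclusion criterion 3 define post-menopausal differently, so a woman not confirmed as non-childbearing can be excused from two-method contraception

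*Protocol*

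**What the plan says.** **Eligibility.** Under inclusion criterion 3 (Section 7.5.1), a woman claiming non-childbearing potential must have it confirmed at screening. The menopausal route is "Post-menopausal defined as amenorrhea for at least 12 months or more following cessation of all exogenous hormonal treatments", together with FSH in the laboratory's post-menopausal range. The other route is documented surgical sterilization.

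**Contraception.** Section 7.4, item 7, sets the duty for women who could become pregnant: they "must use 2 effective methods of avoiding pregnancy, one of which is a barrier method from screening until after the final follow-up visit", which is scheduled for Day 85. Besides surgical sterility, a woman is exempt if she "has a sterile male partner, is 1 year postmenopausal, or practices abstinence". The section then gives its own definition: "Postmenopausal is defined as at least 12 months since last menses and the subject has an elevated" FSH at screening. It does not mention exogenous hormones.

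**Hormones.** The note to exclusion criterion 26 (Section 7.5.2) says "Hormonal replacement therapy is allowed for females". Section 8.7 repeats this for the study period: "For females, hormonal replacement therapy is allowed".

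**Pregnancy tests.** Table 1 (Section 7.2) places them at screening, Day -1 and the final visit. Inclusion criterion 3 requires negative results at screening and on admission for all females.

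**The concern.** Inclusion criterion 3 starts the 12-month count only after every exogenous hormone has stopped. Section 7.4 counts from the last menses, whatever hormones the woman takes. Because hormone replacement is expressly permitted, the protocol admits women for whom the two definitions give different answers.

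Such a woman fails the menopausal route to confirmed non-childbearing status. Failing it does not exclude her. She can be enrolled as a woman of childbearing potential with negative pregnancy tests. Section 7.4 then releases her from contraception on the ground of menopause, the same ground on which inclusion criterion 3 declined to confirm her. Neither section refers to the other. At stake is whether she must use contraception after dosing, during a period with no scheduled pregnancy test.

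**Working it through.** The protocol gives no figure on this point, so the check compares the two definitions as logical conditions and then counts days.

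**1. Conditions**

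- M: at least 12 months since last menses.
- H: those 12 months all fall after stopping exogenous hormones (H can be true only if M is).
- F: FSH post-menopausal at screening. The two sections word this slightly differently; it is treated here as the same condition.

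Section 7.4 requires M and F. Inclusion criterion 3 requires M, H and F. The six feasible combinations are:

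| M | H | F | Post-menopausal under 7.4 | Post-menopausal under inclusion 3 |
|---|---|---|---|---|
| no | no | no | no | no |
| no | no | yes | no | no |
| yes | no | no | no | no |
| **yes** | **no** | **yes** | **yes** | **no** |
| yes | yes | no | no | no |
| yes | yes | yes | yes | yes |

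The definitions disagree in exactly one row: enough time since last menses and a post-menopausal FSH, but hormones are current or were stopped less than 12 months ago. In that row Section 7.4 is the less protective text. No row shows the reverse.

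**2. Can that row occur?** Yes. The age range is 18 to 55 years, hormone replacement is allowed at entry and during the study, and inclusion criterion 3 does not bar women of childbearing potential.

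**3. Days affected**

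- Interval between scheduled pregnancy tests: Day -1 to Day 1 is 1 day and Day 1 to Day 85 is 84 days, so 1 + 84 = 85 days. With the final-visit window of ± 2 days: 83 to 87 days.
- Longest contraception period: 28 days of screening at most, plus Day 1 to Day 85 inclusive (85 days), so 28 + 85 = 113 days. With the window: 111 to 115 days.

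**The case against.** The best defence is that the sections do different jobs. Inclusion criterion 3 governs how non-childbearing status is confirmed at entry; Section 7.4 governs who must use contraception. A site can apply each as written without breaching the other. Section 7.4 also excuses fertile women who are abstinent or have a sterile partner, so being unconfirmed yet exempt is partly how it was designed. This does not settle the matter. Those exemptions rest on a different ground, whereas here a single ground, menopause, is defined twice with different results.

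A second argument is that no real pregnancy risk is shown. Both definitions require FSH, two negative tests precede a single dose, and nothing in the protocol suggests the affected woman is likely to be fertile. That stands and limits the weight of the point. The 85-day interval likewise applies to every female subject tested under Table 1, and the fix does not shorten it. It describes the setting and does not measure the discrepancy.

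Third, under the stricter definition a non-sterilized woman on continuous hormone replacement could never count as post-menopausal, so she would need two methods unless abstinent or with a sterile partner. This is a genuine cost of the fix.

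Finally, the surgical-sterility lists also differ: Section 7.4 omits bilateral salpingectomy and tubal occlusion. There Section 7.4 is the stricter text, so this is a separate matter of tidiness.

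**Conclusion.** The inconsistency is real and follows directly from the text. For one profile of woman, the protocol does not confirm non-childbearing status but excuses her from contraception as post-menopausal, and it does not say which definition prevails.

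The effect is small. The protocol gives no count of such women, and there may be none among 30 subjects. Women who are surgically sterile under Section 7.4, abstinent or with a sterile partner are unaffected. Sample size, endpoints and analyses do not change. The conclusion assumes that the two FSH wordings are equivalent in practice and that a site applies Section 7.4 literally. It is a low-priority improvement to participant protection.

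**What to change.** Change two pieces of wording in Section 7.4, item 7:

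- Replace the definition with a cross-reference: *Postmenopausal is defined as in inclusion criterion 3.*
- Change the menopausal exemption to: *is post-menopausal per inclusion criterion 3.*

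This adopts the stricter definition the sponsor has already written, which suits healthy volunteers who gain no direct benefit (Section 5.6). No other section, visit or procedure needs to change. The cost is that a few women, possibly none, including any non-sterilized woman on continuous hormone replacement, would have to use contraception they would otherwise be excused from.
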